8.3 STUDY POPULATION AND PLANNED ANALYSIS

8.3.1 Populations

8.3.1.1 Safety population

The safety population includes the subjects who satisfy all inclusion/exclusion criteria, are randomized and received at least single dose of study medication.

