Safety analyses will be based on the Safety population which will consist of all patients who are known to have received at least 1 dose of study treatment, with patients grouped according to the actual treatment received.

All safety endpoints (AEs, clinical laboratory testing, ECG, body weight, physical examination and vital signs) will be summarized by treatment group using the following descriptive statistics: N, mean, median, standard deviation, minimum and maximum for continuous variables, and patient counts and percentages for categorical variables.

ABBREVIATIONS

Abbreviation	Definition
AASLD	American Association for the Study of Liver Disease
ADRs	Adverse drug reactions
AE	Adverse event
ALP	Alkaline phosphatase
ALT	Alanine aminotransferase
AMA	Antimitochondrial antibodies
ANA	Anti-nuclear antibody
ANCOVA	Analysis of Co-variance
API	Active pharmaceutical ingredient
aPTT	Activated partial thromboplastin time
AST	Aspartate aminotransferase
BMI	Body mass index
BP	Blood pressure
C4	7 α -hydroxy-4-cholesten-3-one
CI	Confidence interval
CIOMS	Council for International Organizations of Medical Sciences
CAP	College of American Pathologist
CFR	Code of Federal Regulation
CRA	Clinical research associate
CRF	Case report form
CRO	Contract research organisation
CLIA	Clinical Laboratory Improvement Amendments
C _{max}	Maximum serum concentration
CSR	Clinical Study Report
CYP	Cytochrome
DPP-4	Dipeptidyl peptidase 4
EASL	European Association for study of the Liver
ECG	Electrocardiogram
ECI	Events of clinical interest
eCRF	Electronic case report form
eGFR	Estimated glomerular filtration rate
EDC	Electronic data capture
EPICS	Evaluation in primary biliary cholangitis with Saroglitazar magnesium
FGF 19	Fibroblast growth factor 19
FPG	Fasting plasma glucose
GCP	Good Clinical Practice
GGT	Gamma glutamyltransferase
HBV	Hepatitis B virus
HCV	Hepatitis C virus

Abbreviation	Definition
HDL	High density lipoprotein
HIV	Human Immunodeficiency Virus
ICH	International Council for Harmonisation
ICF	Informed consent form
IEC	Independent Ethics Committee
[Ig]M	Immunoglobulin M
IP	Investigational product
INR	International Normalized Ratio
IRB	Institutional Review Board
IUD	Intrauterine device
LDL	Low density lipoprotein
LOCF	Last observation carried forward
MedDRA	Medical Dictionary for Regulatory Activities
MITT	Modified Intent-to-treat
NASH	Non-alcoholic steatohepatitis
PBC	Primary Biliary Cholangitis
PP	Per-protocol
PPAR	Peroxisome proliferator-activated receptors

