7.5 PROTOCOL DEVIATIONS

For the purposes of this study, no distinction will be made between Protocol Violations and Deviations. Deviations may be categorized as minor protocol deviation and a major protocol deviation. Minor protocol deviation includes any deviations that do not necessarily influence

**Zydus Discovery
DMCC**

CLINICAL TRIAL PROTOCOL

Saroglitazar Magnesium – Phase II

SARO.16.004

CONFIDENTIAL

PAGE 55 OF 82

the results/outcome of primary endpoints or subject safety. Minor protocol deviations do not require immediate notification to the IEC/IRB unless otherwise specified by IEC/IRB requirements. All minor protocol deviations will be noted in monitoring reports and provided to the investigator.

Major protocol deviation includes any violation which may influence the results/outcome of primary endpoints or subject safety. Major protocol deviations must be reported immediately to the IRB/IEC as specified by the IRB/IEC requirements. All Major protocol deviations will be reported to the Sponsor immediately.

Note: persistent non-compliance of minor protocol deviations may rise to the level of major protocol deviations.

The Sponsor reserves the right to terminate the study at a given center in the event of monitoring and/or auditing findings of serious or persistent non-compliance with the protocol, SOPs, GCP, and/or applicable regulatory requirement(s) by an investigator/institution. In all case of site closure due to protocol deviations, the IEC/IRB and regulatory authority will be informed.

The clinical study report will provide the list of protocol deviation/violation on separate section. The result will be analysed for all participants with major protocol deviations.

Protocol deviation/violation will include but are not limited to the following;

- Subjects that did not meet entry criteria
- Subjects that developed withdrawal criteria but were not withdrawn
- Subjects that received the wrong treatment or incorrect dose
- Subjects that received an excluded medication

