8.3.3 Safety Analysis

All safety analysis will be carried out on safety population. The frequency tabulations of abnormal clinical laboratory values for the parameter will be presented for each treatment group by visit. Summary statistics for clinical laboratory parameters, ECG, physical examination and vital signs will be presented for each treatment by visit.

All AEs seen during the study period will be listed. Incidence of all AEs reported during the study will be summarized using the Medical Dictionary for Regulatory Activities (MedDRA) (version 19 or higher) by treatment group, body system, frequency, severity, seriousness, and relationship to study drug and expectedness.

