3.2 Safety Analysis Population

The safety population includes the subjects who are randomized and received at least single dose of study medication. For safety analyses, subjects will be analyzed according to the actual treatment received.

Document Title:	Statistical Analysis Plan		
Version Number:	2.0	Date:	11 Nov 2019
Protocol Number:	SARO.16.004	Sponsor Name:	Zydus Discovery DMCC

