8.3.2 Adverse Events

The applicable definition of an Adverse Event (AE) is in the study protocol. All AEs occurring from when a patient signs informed consent to when a patient exits the study will be accounted for in the reporting. Analysis and presentation of AEs occurring during the screening period will be separated from those occurring during the investigational period where a comparative evaluation of treatment-emergent AEs is intended. A treatment-emergent AE is an event not present prior to exposure to investigational product or any pre-existing event that worsens following exposure to investigational product. The period for treatment-emergent AE analysis starts from the first exposure to the investigational product until the patient exits the study.

Descriptive summaries (frequencies and percentages) for specific AEs will be presented by system organ class and preferred term according to the Medical Dictionary for Regulatory Activities (MedDRA Version 19.1) dictionary by treatment group and overall. In addition to an overall presentation of all AEs, reports will be generated for special classes of AEs such as investigational product related AEs, serious AEs, Maximum severity and AEs resulting in treatment discontinuation by treatment group. These reports will be supported by individual patient listings, as necessary.

Document Title:	Statistical Analysis Plan		
Version Number:	2.0	Date:	11 Nov 2019
Protocol Number:	SARO.16.004	Sponsor Name:	Zydus Discovery DMCC

Adverse events will be counted by the number of events as well as the number of subjects. For the summaries which count the number of patients by treatment group and overall, multiple AEs with the same MedDRA preferred term within the same patient will only be counted once.

Descriptive summaries (frequencies and percentages) for number of subjects experiencing AEs will also be presented.

Only patient listings will be provided for AEs that occur after signing informed consent but prior to exposure to investigational product. These listings will comprise all events occurring during this period in any patient who consented to participate in the study.

These listings will at least contain but not limited to information such as onset and resolution times, maximum severity, causal relationship to study treatment and action taken.

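### Protocol 8.3.1.1 makes full eligibility a condition of the safety population, while the protocol synopsis and SAP 3.2 do not, and the conflict is unreconciled

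*Protocol*

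**What the plan says.** Three current texts define the safety population.

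- Protocol 8.3.1.1: "The safety population includes the subjects who satisfy all inclusion/exclusion criteria, are randomized and received at least single dose of study medication". It does not say how patients are grouped by treatment.
- Protocol synopsis, Safety Analysis: a "Safety population which will consist of all patients who are known to have received at least 1 dose of study treatment", grouped by the treatment actually received.
- SAP 3.2: "The safety population includes the subjects who are randomized and received at least single dose of study medication", again analysed by actual treatment.

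Protocol 8.3.3 ties the analysis to the set: "All safety analysis will be carried out on safety population". The same section adds, without naming a population, "All AEs seen during the study period will be listed". SAP 8.3.2 goes further: "All AEs occurring from when a patient signs informed consent to when a patient exits the study will be accounted for in the reporting".

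The protocol foresees patients who enter without being eligible. The deviation list in 7.5 begins with "Subjects that did not meet entry criteria", and withdrawal criterion 2 in section 4.4 lets the investigator withdraw a subject who entered in breach of the protocol.

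**The concern.** A safety set is normally everyone exposed to study treatment, because a dosed patient's safety experience is informative whether or not the patient should have been enrolled. Protocol 8.3.1.1 makes the set depend on eligibility, a condition that otherwise belongs to the per-protocol set (8.3.1.3). The modified intent-to-treat set (8.3.1.2) has no such condition. Read literally, the protocol body would let an ineligible dosed patient count towards efficacy but not towards safety.

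At stake are the denominators and content of the summaries by treatment group: adverse event incidence, abnormal laboratory values, ECG, vital signs and physical examination. In arms of 12, one patient changes these visibly. The conflict also sits inside the protocol itself, between synopsis and body, so it remains whatever the SAP says.

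**Working it through.** The plan states no figure to reproduce here. The check is a comparison of definitions, followed by simple arithmetic for scale.

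**1. Definitions side by side**

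| Set and source | Eligible | Randomized | At least one dose | Post-randomization efficacy measurement | Grouping stated |
|---|---|---|---|---|---|
| Safety, protocol 8.3.1.1 | required | required | required | no | not stated |
| Safety, protocol synopsis | no | no | required | no | actual treatment |
| Safety, SAP 3.2 | no | required | required | no | actual treatment |
| MITT, protocol 8.3.1.2 | no | required | required | required | not stated there |

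Only the first row carries an eligibility condition. The synopsis and the SAP differ from each other only on randomization. Protocol 5.6 places the first dose after randomization, so that difference matters only if someone is dosed in error.

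**2. One patient traced through the rules**

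Take a patient who is randomized and dosed, has one post-randomization ALP value, and is then found to breach an exclusion criterion.

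- MITT: included.
- Safety under the synopsis or SAP 3.2: included.
- Safety under protocol 8.3.1.1: excluded, and so outside the safety summaries under 8.3.3.
- Adverse event listing: the 8.3.3 sentence on listing has no population limit, so the events still appear there.

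**3. Which text applies**

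Neither document states an order of precedence. Protocol 8.1 leaves the detailed safety analysis to the SAP. SAP version 2.0 (11 Nov 2019) is based on protocol version 6.0 (21 August 2019). It does not flag its departure from 8.3.1.1; its revision history mentions only the interim analysis. SAP 8.3 then sends the reader to Section 2.2 for the safety set. Section 2.2 is the study description, and the definition is in 3.2. SAP 8.2 has a similar slip: it points to 6.1 for safety endpoints that are listed in 8.1. This looks like stale numbering rather than a different intention.

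**4. Scale (illustration only)**

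Inputs: 12 patients per arm (protocol 8.5, SAP 4). The number of dosed but ineligible patients in an arm is an assumption, taken as 1 or 2, because the documents give none.

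- One patient: 1/12 = 8.3% of the arm. Two patients: 2/12 = 16.7%.
- If the dropped patient had the arm's only case of an event, incidence goes from 1/12 = 8.3% to 0/11 = 0%.
- If the dropped patient had no event and another patient in the arm did, incidence goes from 1/12 = 8.3% to 1/11 = 9.1%.

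Under the synopsis or SAP definition, no randomized and dosed patient is dropped for ineligibility.

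**The case against.** The best defence is that the analysis actually specified is sound. SAP 3.2 has no eligibility condition, the SAP postdates the protocol version it is based on, protocol 8.1 defers to it, and the synopsis agrees with it. A programmer working from SAP 3.2 would include every randomized, dosed patient. This stands, and it limits the practical risk. It does not remove the contradiction between the protocol's own synopsis and body.

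A reader might infer more than the documents support, in three ways.

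- *That ineligible patients will be left out of the safety analysis because the protocol governs.* Exclusion follows only if 8.3.1.1 is applied over the synopsis and the SAP, and no text gives it that priority.
- *That their adverse events would vanish.* Protocol 8.3.3 lists all events, and SAP 8.3.2 accounts for all events from consent to exit. Protocol 8.3.3 also speaks of summarizing the incidence of all reported events, which can be read either way against its opening sentence. Protocol 7.5 promises analysis of participants with major deviations. One limit on this reassurance: the interim analysis (SAP 2.5) summarizes adverse events without subject-level listings.
- *That the safety profile would be biased favourably.* Exclusions 5 to 9 do concern INR, bilirubin, worsening liver tests or INR, creatinine, CK, lipase and amylase, so higher risk in some violators is a fair inference. But other criteria concern UDCA duration, diagnosis, the ALP threshold or previous trial participation, and the condition would remove placebo patients too. The net direction is unknown. Nor does the upper confidence bound help that argument. For an event not seen, the one-sided 95% bound is 1 − 0.05^(1/n): 22.1% at n = 12 and 25.9% at n = 10. Fewer patients make it less reassuring, not more.

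**Conclusion.** The definition in protocol 8.3.1.1 is wrong as written and conflicts with the synopsis of the same protocol and with SAP 3.2. This follows from the text and needs no assumption. The effect on results is conditional: it arises only if 8.3.1.1 is applied and at least one dosed patient proves ineligible. It would then touch the safety summaries and denominators, at 8.3% of a 12-patient arm per patient, with the events still listed. How often this would happen, and in which direction it would push a comparison between arms, cannot be determined from the documents. The practical risk is limited because SAP 3.2 already uses all randomized, dosed subjects. This should be corrected, but it does not undermine the planned safety analysis.

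**What to change.** In protocol 8.3.1.1, delete the condition on inclusion/exclusion criteria and add that subjects are analysed according to the treatment actually received. Deletion alone is not enough, since the section never stated the grouping. A suitable text would be: *All randomized subjects given one or more doses of study medication, analysed according to actual treatment received.* This matches SAP 3.2 and agrees with the synopsis on eligibility and treatment grouping.

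In SAP 8.3, change the cross-reference for the safety set from Section 2.2 to Section 3.2.

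The cost is a few words in the next protocol amendment and one number in the SAP. No clinical procedure, data collection or sample size changes.

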8.3.1.2 Modified intent-to-treat population

The modified intent-to-treat (MITT) population includes: all randomized subjects who received any study drug and have at least one post-randomized efficacy measurement.

All primary and secondary objectives will be analysed using MITT population with LOCF method. Last observation carried forward (LOCF) method will be used as an imputation method for the efficacy variables for MITT analysis.

 Zydus Discovery DMCC	CLINICAL TRIAL PROTOCOL Saroglitazar Magnesium – Phase II SARO.16.004	CONFIDENTIAL PAGE 57 OF 82
---	---	---

8.3.1.3 Per-protocol population (PP)

The per-protocol population (PP) includes all randomized patients who meet all the inclusions/exclusion criteria, completed the treatment phase and have not deviated from or violated the protocol in such a way that could affect efficacy outcome.

8.3.2 Planned Analysis

Modified intent-to-treat (MITT) and Per Protocol (PP) analysis will be carried out for the efficacy analysis.

All efficacy analyses will be based primarily on the MITT, and analyses based on the Per Protocol (PP) analysis set will be secondary to this.

The MITT will consist of all patients who have been randomized, taken at least 1 dose of the study treatment and have provided at least a post-randomized efficacy data. Missing values will be imputed by carrying forward the last observation value after baseline.

8.3.2.1 Primary Efficacy Analysis

The primary analysis for the primary efficacy endpoint will be based on the MITT. The primary efficacy endpoint in this study is improvement in ALP levels after 16 weeks in Saroglitazar magnesium treatment.

The primary endpoint will be summarized and improvement from baseline to week 16 will be evaluated using Paired t-Test. Statistical significance will be defined as a p-value <0.05.

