4.2 INCLUSION CRITERIA

1. Males or females, between 18 and 75 years of age, inclusive.
2. a) Patients on therapeutic doses of Ursodeoxycholic acid (UDCA) for ≥ 12 months and stable therapy for ≥ 3 months prior to enrolment.
OR
b) Patients who are unable to tolerate UDCA, and did not receive UDCA for at least 3 months from the date of screening.
3. History of confirmed Primary Biliary Cholangitis Diagnosis, based on American Association for the Study of Liver Disease [AASLD] and European Association for Study of the Liver [EASL] Practice Guidelines; [Lindor 2009; EASL 2009], as demonstrated by the presence of at least ≥ 2 of the following 3 diagnostic factors:
 - History of elevated Alkaline Phosphatase levels for at least 6 months prior to Screening Visit 1
 - Positive antimitochondrial antibodies (AMA) titer or if AMA negative or in low titer ($<1:80$) PBC specific antibodies (anti-GP210 and/or anti-SP100 and/or antibodies against the major M2 components [PDC-E2, 2-oxo-glutaric acid dehydrogenase complex])
 - Liver biopsy consistent with PBC.

4. ALP $\geq 1.67 \times$ upper limit of normal (ULN) at Visit 1 and Visit 2 and with $< 30\%$ variance between the levels from Visit 1 to Visit 2.
5. Contraception: Female patients must be postmenopausal, surgically sterile, or if premenopausal, agree to use ≥ 1 effective method of contraception during the trial. Effective methods of contraception are considered to be Hormonal (e.g., contraceptive pill, patch, intramuscular implant or injection); or Double barrier method, i.e., (a) condom (male or female) or (b) diaphragm, with spermicide; or Intrauterine device (IUD); or Vasectomy (partner).
6. Must provide written informed consent and agree to comply with the trial protocol.

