7 INVESTIGATIONAL PLAN

7.1 STUDY DESIGN AND PLAN

This is a Phase 2 prospective, multicentre, randomized, double-blind, placebo-controlled study includes a total 36 patients with a diagnosis of Primary Biliary Cholangitis. The study will be conducted over a period of up to 26 weeks and will include a 6-week Screening Phase, a 16-week Treatment Phase and a safety follow-up visit after 4 weeks.

Screening Phase:

- Visit 1 (Day -42): Patient eligibility for participation in the study will be assessed. Medical history will be obtained and physical examination, electrocardiogram (ECG) and laboratory evaluations (including serology, [anti-nuclear antibody, smooth muscle antibody and serum immunoglobulin level G], clinical chemistry, hematology, liver biochemistries, and urinalysis) will be performed. In patients with ANA or SMA antibody positive titers, a liver biopsy must have been performed to rule out autoimmune hepatitis or overlap syndrome. Female patients will undergo a pregnancy test. Serum ALP must be ≥ 1.67 upper limit of normal (ULN) to proceed further in the study.
- Visit 2 (Day -14 to -7): Liver biochemistries (ALT, ALP, total bilirubin (TB) and INR will be re-measured approximately 4 weeks from Day -42 to determine eligibility. Elevated ALP must be ≥ 1.67 ULN on 2 occasions in the Screening Phase and is necessary for study entry. If there is an increase of more than 30% in the levels of ALT, total bilirubin or INR at Day (-14) to Day (-7) [Visit 2] as compared to the values on Day (-42) [Visit 1], then such patients will not be eligible for study entry. The average of two assessments (Visit 1 and Visit 2) of liver biochemistries and INR will be considered as baseline values for these parameters.

Randomization & Treatment Phase:

- Visit 3: The Randomization & Treatment Phase will include 6 outpatient visits over a period of 16 weeks, including the randomization visit. Patients will be randomly assigned to receive either Saroglitzaz magnesium (2 mg or 4 mg) or placebo orally

once daily in addition to their ongoing treatment with UDCA (Patients unable to tolerate UDCA will receive only the investigational medicinal products), starting on Day 1 and continuing for 16 weeks. Efficacy and safety parameters will be assessed during each study visit as per the Schedule Visit Table 1.

- Visit 3.1: Patient will visit study site at 2 weeks after randomization visit for LFTs. The LFTs will be performed at local laboratory.

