8.2 NULL AND ALTERNATIVE HYPOTHESIS

Below is the hypothesis of primary efficacy endpoint:

Null hypothesis: $H_0: \mu_s = 0$

Alternative hypothesis $H_1: \mu_s > 0$

Where: μ_s = change from baseline in ALP levels of the Saroglitazar magnesium (2 mg and 4 mg).

Rejection of the null hypothesis will lead to conclude that the change from baseline in Saroglitazar magnesium 2 mg and 4 mg is statistically significant and hence the test drug is effective.

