8.3.2.2 Secondary Efficacy Analysis

Each secondary efficacy endpoint will be summarized by treatment group at each time point, as appropriate.

Following secondary endpoints will be analyzed:

- Change from baseline in ALP at Week 4, Week 8, Week 12 and Week 16 in Saroglitazar magnesium as compared to placebo.

Approved by: [name]	Protocol No. SARO.16.004 Version No.: 6.0
----------------------------------	--

- Change from baseline in lipid profile (TG, TC, HDL, LDL, and VLDL) at Week 4, Week 8, Week 12 and Week 16 in Saroglitzaz magnesium as compared to placebo.
- Change from baseline in liver biochemistries (GGT, ALT, AST, bilirubin and albumin) at Week 4, Week 8, Week 12 and Week 16 in Saroglitzaz magnesium as compared to placebo.
- Change from baseline in serum total bile acids at Week 4, Week 8, Week 12 and Week 16 in Saroglitzaz magnesium as compared to placebo.
- Change from baseline in 7α -hydroxy-4-cholesten-3-one (C4) and fibroblast growth factor 19 (FGF 19) at Week 16 in Saroglitzaz magnesium as compared to placebo.
- Proportion of patients with ALP improvement, i.e. 15%, 20%, 30%, 40% and normalization at Week 8 and Week 16.
- Change in QoL at Week 16 by using PBC40.
 - This instrument consists of 6 domain and 40 questions: symptoms, itch, cognition, emotion and social.
- Change from baseline in ALP in patients who are unable to tolerate UDCA at week 16 in Saroglitzaz 2 mg and 4 mg as compared to Placebo.
- Pharmacokinetics of Saroglitzaz.

The change from baseline will be determined as:

Change = (Post-baseline – Baseline)

Percent Change = (Post-baseline – Baseline) / Baseline * 100

Treatment effects will be estimated using the least-square mean, standard error and 95% confidence intervals from ANCOVA model with baseline value as covariate. Comparison will be done for Saroglitzaz magnesium (2 mg and 4 mg) and placebo using the difference in least-square means from the ANCOVA model. Proportion of patients with ALP

improvement, i.e., 15%, 20%, 30%, 40% and normalization at Week 8 and Week 16 will be presented as counts and percentages.

Descriptive statistics will be provided for each pharmacokinetic parameter.

The following pharmacokinetic parameters will be evaluated:

- i. Peak Plasma concentration (Cmax)
- ii. Time to reach peak Plasma concentration (Tmax)
- iii. Area under Plasma concentration vs. time curve till the last time point (AUC0-t)

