6.2 Efficacy Endpoints

Primary Endpoint:

The primary efficacy endpoint is the change from baseline in alkaline phosphatase (ALP) at Week 16 in Saroglitzazar magnesium (2 mg and 4 mg) treatment.

Document Title:	Statistical Analysis Plan		
Version Number:	2.0	Date:	11 Nov 2019
Protocol Number:	SARO.16.004	Sponsor Name:	Zydus Discovery DMCC

Secondary Endpoints:

The following secondary efficacy endpoints will be evaluated in Saroglitzazar magnesium (2 mg and 4 mg) treatment as compared to placebo:

- Change from baseline in ALP at Week 4, Week 8, and Week 12 and Week 16.
- Change from baseline in lipid profile (TG, TC, HDL, LDL and VLDL) at Week 4, Week 8, Week 12 and Week 16.
- Change from baseline in liver biochemistries (GGT, ALT, AST, bilirubin and albumin) at Week 4, Week 8, Week 12 and Week 16.
- Change from baseline in serum total bile acids at Week 4, Week 8, Week 12 and Week 16.
- Change from baseline in 7 α -hydroxy-4-cholesten-3-one (C4) at Week 16
- Change from baseline in fibroblast growth factor 19 (FGF 19) at Week 16.
- Proportion of subjects with ALP improvement of 15%, 20%, 30%, 40% and normalization at Week 8 and Week 16.
- Change from baseline in QoL at Week 16 by using PBC-40.
- Safety and tolerability of Saroglitzazar magnesium 2 mg and 4 mg.
- Pharmacokinetics of Saroglitzazar.

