6.3 Efficacy Hypotheses

The statistical hypothesis to test the primary efficacy endpoint, change in ALP from baseline to Week 16 for Saroglitzazar magnesium 2 mg and Saroglitzazar magnesium 4 mg are:

$$H_0: \mu_s \leq 0$$

$$H_1: \mu_s > 0$$

Where μ_s = change from baseline in ALP levels for Saroglitzazar magnesium 2 mg or Saroglitzazar magnesium 4mg.

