6.4 Statistical Methods for Efficacy Analyses

The primary efficacy endpoint, change from baseline in ALP value at Week 16 will be analyzed separately for Saroglitzazar magnesium 2 mg and 4 mg using a two-sided paired t-test. The primary analysis will be performed using MITT population with LOCF as imputation method for missing values.

The analysis for the secondary efficacy endpoints, change from baseline in ALP at Week 4, Week 8, Week 12 and week 16, change from baseline in lipid profile (TG, TC, HDL, LDL, and VLDL), liver biochemistries (GGT, ALT, AST, bilirubin and albumin), serum total bile acids, 7 α -

Document Title:	Statistical Analysis Plan		
Version Number:	2.0	Date:	11 Nov 2019
Protocol Number:	SARO.16.004	Sponsor Name:	Zydus Discovery DMCC

hydroxy-4-cholesten-3-one (C4) and fibroblast growth factor 19 (FGF 19) and change from baseline in QoL (PBC40) total scores will be analyzed using ANCOVA (Analysis of covariance) model using baseline values and treatment as factors. The p-value for the treatment comparison, estimate of LSMEANS treatment difference (Saroglitazar magnesium (2 mg and 4 mg) – Placebo), and the 95% confidence interval of the LSMEANS difference will be generated from ANCOVA model. Observed and change from baseline values will be summarized descriptively at each visit for all secondary efficacy endpoints.

Frequency and percentage of subjects with ALP improvement of 15%, 20%, 30%, 40% and normalization (achieving abnormal to normal values) at Week 8 and Week 16 will be presented. Difference between the treatment groups will be presented using 95% exact confidence Interval for proportion.

For the PBC40 questionnaire responses, descriptive summaries will be provided for the total and also for each dimensional score.

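### The primary test compares each saroglitazar arm only with its own baseline, yet the Protocol concludes from it that the drug is effective; the randomised placebo arm plays no part in that inference

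*Protocol*

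**What the plan says.** - **Endpoint.** SAP 6.2 defines the primary endpoint as the ALP change from baseline "at Week 16 in Saroglitzazar magnesium (2 mg and 4 mg) treatment". Protocol 6.1.1 likewise names only the two active doses.
- **Hypothesis.** In SAP 6.3 the tested parameter is the "change from baseline in ALP levels for Saroglitzazar magnesium 2 mg or Saroglitzazar magnesium 4mg". Protocol 8.2 also defines it for the active drug only. Neither has a placebo term.
- **Test.** Protocol 8.3.2.1: "improvement from baseline to week 16 will be evaluated using Paired t-Test", at p<0.05. SAP 6.4 analyses 2 mg and 4 mg separately "using a two-sided paired t-test". The Protocol itself does not say whether the doses are tested separately or pooled.
- **Conclusion.** Protocol 8.2 states that rejection shows the change "is statistically significant and hence the test drug is effective".
- **Where placebo enters.** Protocol 8.3.2.2 compares each dose with placebo "using the difference in least-square means from the ANCOVA model", with baseline as covariate. SAP 6.4 adds a p-value and a 95% confidence interval. These analyses include ALP at Week 16 but are secondary.
- **Baseline.** Protocol 7.1: "The average of two assessments (Visit 1 and Visit 2) of liver biochemistries and INR will be considered as baseline values for these parameters". Under Protocol 4.2 both of those ALP values must be at least 1.67 × ULN, with less than 30% "variance between the levels from Visit 1 to Visit 2".

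**The concern.** The paired t-test answers whether mean ALP in an arm at Week 16 differs from baseline. Protocol 8.2 uses it to answer whether the drug works. The two questions coincide only if ALP would not have moved without the drug, and the placebo arm was randomised so that nobody has to assume that.

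Any fall shared by all arms counts towards the drug under the stated rule. One source is visible in the plan: regression to the mean, because baseline is built from the same two values that had to clear the entry threshold. Better adherence to UDCA, a time trend or laboratory drift would act in the same way.

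Read literally, a significant paired test alongside no difference from placebo would still end in a statement of effectiveness. That is the trial's main efficacy conclusion, and the trial is meant to inform phase III.

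**Working it through.** **The plan's own figure.** The sample size is 3 × 12 = 36. SAP 4 says no formal estimation was done, so there is no effect size, SD or power to reproduce. Protocol 4.1 says the 36 include 20% dropout: 36 × 0.8 = 28.8 completers, or 9.6 per arm. Results are therefore given for 12 and 10 per arm.

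**Step 1: a change shared by all arms.** Let every arm, placebo included, change by δ standard deviations of the change score, with no drug effect. The paired statistic is t = d̄ / (s_d/√n) with n − 1 df and noncentrality δ√n. For two independent arms tested at two-sided 0.05, P(either) = 1 − (1 − p)². With n = 12:

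| Shared change δ (assumed) | Rejects, per dose | Rejects, either dose |
|---|---|---|
| 0 | 5.0% | 9.8% |
| 0.2 | 9.7% | 18.5% |
| 0.3 | 15.8% | 29.1% |
| 0.5 | 35.3% | 58.1% |
| 0.8 | 71.4% | 91.8% |

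For example, at δ = 0.5 the noncentrality is 0.5 × √12 = 1.73, and 1 − (1 − 0.353)² = 0.581. The three-arm ANCOVA with baseline covariate, simulated at δ = 0, 0.5 and 0.8, rejects in about 5% per comparison and 9% for either dose. At δ = 0 the paired test holds its level, so the test is sound for its own null; the fault is in what is concluded from it.

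**Step 2: the plan's entry rule and baseline.** From the documents: both screening ALP values ≥ 1.67 × ULN, a difference below 30%, baseline equal to their mean, and 12 per arm. Assumed, because the documents give none of it:
- median true ALP before selection 1.7, 2.0 or 2.5 × ULN;
- between-patient log-SD 0.4 or 0.5;
- within-patient log-SD 0.10, 0.15 or 0.20;
- non-drug fall 0, 5% or 10%, the same in every arm.

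This gives 3 × 2 × 3 = 18 settings, each simulated with 20,000 trials. Week 16 ALP = true value × (1 − non-drug fall) × noise. Only significant falls are counted, so the nominal rate is 2.5% per dose and 1 − 0.975² ≈ 4.9% for either dose.

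| Non-drug fall | Paired, per dose, n = 12 | Paired, either dose, n = 12 | Paired, per dose, n = 10 |
|---|---|---|---|
| 0 (selection only) | 3–6% | 6–13% | 3–6% |
| 5% | 11–33% | 21–55% | 10–28% |
| 10% | 29–81% | 49–97% | 24–73% |

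The ANCOVA against placebo gives 2.2–2.6% per dose at n = 12 and 2.3–2.6% at n = 10.

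Selection alone is modest because two values must both be high and must agree. In a less favourable case (median 1.5 × ULN, between-patient log-SD 0.30, within-patient log-SD 0.18) it reaches about 11% per dose.

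**Step 3: what the controlled comparison costs in power.** For 80% power at two-sided 0.05, solve for δ with noncentrality δ√n and n − 1 df (paired), or δ√(n/2) and 2n − 2 df (two-sample):

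| n per arm | Paired, within arm | Two-sample, against placebo |
|---|---|---|
| 12 | 0.89 SD | 1.20 SD |
| 10 | 1.00 SD | 1.32 SD |

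These are before any gain from the covariate. Under the Step 2 variances with 12 per arm, ANCOVA power is 32–87% for a true 15% fall, 54–99% for 20% and 90–100% for 30%; these are three of the plan's own ALP improvement thresholds. At a 15% fall the paired test has 55–99%.

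**The case against.** **Placebo is not ignored.** The Week 16 ALP difference, with p-value and interval, is planned for both doses, and SAP 6.4 adds responder differences with exact intervals. This is correct: the criticism applies to the primary test and its conclusion, not to the whole plan. But no section makes the conclusion depend on those results.

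**The test matches the primary objective.** Protocol 3.1 asks about the effect of the two doses on ALP, and comparison with placebo is a secondary objective. An effect of a regimen is, however, a causal claim, and Protocol 8.2 goes on to declare effectiveness.

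**It is a proof-of-concept trial.** That explains the small sample and the absence of multiplicity adjustment. It does not justify a causal conclusion from an uncontrolled contrast when a concurrent control exists.

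**The large error rates are assumed.** This stands. The only non-drug mechanism the documents show is screening selection, and it is modest. Long-standing UDCA at a stable dose, fixed concomitant doses and a two-visit baseline all limit drift. The 5% and 10% falls show sensitivity; they are not predictions. The ANCOVA stays level because the fall is set equal in all arms, which is what randomisation is expected to deliver.

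**Ten per arm is pessimistic.** This also stands. MITT with LOCF keeps any dropout with a post-baseline value. The 12-per-arm figures are the main ones.

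**A smaller remedy exists.** Tying the sentence in Protocol 8.2 to the ANCOVA would remove the faulty inference. It would leave the trial with a primary test that no longer decides its efficacy question, so it is a minimum rather than the better solution.

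**Conclusion.** The concern holds, and the change is needed. The primary endpoint, hypothesis and test involve only the saroglitazar arms, and Protocol 8.2 turns a within-arm change into a finding of effectiveness. Followed as written, the plan can declare the drug effective with no difference from placebo.

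The logical fault depends on no assumed number. Its practical size does: slight if screening selection is the only non-drug influence, large if ALP falls by 5–10% for other reasons. The documents support neither of those falls and rule out neither. A comparison with placebo removes the dependence on any non-drug change that is common to the arms.

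**What to change.** - **Primary analysis.** In Protocol 6.1.1, 8.2 and 8.3.2.1 and SAP 6.2–6.4, make the Week 16 ALP least-squares mean difference from placebo, for each dose, the primary analysis. Use the ANCOVA with baseline covariate that is already planned.
- **Hypotheses and conclusion.** Restate the hypotheses as differences from placebo, and make the effectiveness conclusion in Protocol 8.2 depend on that test.
- **Paired tests.** Keep them as descriptive within-arm summaries.
- **Conforming edits.** Align the synopsis, Protocol 3.1, 3.2, 6.1.2 and 8.3.2.2 and SAP 2.1, so that Week 16 ALP against placebo is not listed as both primary and secondary.
- **Timing.** Make the change before the interim unmasking described in Protocol 8.3.5 and SAP 2.4–2.5. If that has already taken place, record that those making the change had not seen unmasked results.

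**Cost.** One protocol amendment and one SAP revision, with no new visits, data or analysis methods. The real cost is power: the detectable effect rises by about a third (1.20/0.89 = 1.35 with 12 per arm) before covariate gain, and a true 15% fall may well be missed. Since no sample-size calculation was made, no stated power is broken.
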